5.3.3. Handling of Missing and/or Unquantifiable Immune Response Data

Missing immune response data will not be imputed.

Values below the lower limit of quantification (LLOQ) will be imputed based on the type of analysis:

- Values below LLOQ will be imputed to LLOQ/2, except for the calculation of the geometric mean of the increase from baseline where values below LLOQ will be imputed to LLOQ.
- Values above the upper limit of quantification (ULOQ) will be imputed with the ULOQ.

The ULOQ and LLOQ values per assay will be available in the database.

5.4. Secondary and Exploratory Endpoint(s) Analysis

5.4.1. Secondary and Exploratory Immunogenity Endpoint(s)

5.4.1.1. Definition of Endpoint(s)

The secondary immunogenicity endpoint is the neutralizing antibody titers against RSV A2 strain (VNA A2) at 14 days after vaccination.

The exploratory immunogenicity endpoints are:

- pre-F ELISA antibody titers at 6 months after vaccination
- VNA A2 at 6 months after vaccination

5.4.1.2. Analysis Methods

Pre-F ELISA and VNA A2 titers will be summarized with descriptive statistics. Descriptive statistics (N, geometric mean[§] and corresponding 95% CI) of the actual values will be calculated for continuous immunogenicity parameters at all timepoints. Geometric mean[§] fold increases from baseline and corresponding 95% CIs might additionally be calculated. §calculate the mean and corresponding 95%CI of the log₂-transformed values, back-transform this mean [i.e. 2^mean] and CI [i.e. 2^CI].

The tables will also show the fold increases from baseline together with the percentage of participants with an x-fold increase from baseline (for several values of x).

Actual values and fold changes from baseline will also be presented in dot-plots with dots for participant values, and the corresponding geometric mean and 95% CI per timepoint for each assay. In addition, plots of GMT over time, combining the regimens in one graph (without individual participant dots) will be created. Participant profiles of the actual values over time will be graphically presented. Reverse distribution curves of the actual values will be provided for selected timepoints. In the graphs, original values will be displayed on the log₂ scale.

GMRs (GMT_{Group 2}/GMT_{Group 1} and GMT_{Group 3}/GMT_{Group 1}) will also be calculated for VNA A2 in a similar manner as for pre-F ELISA.

Refer to Section 5.3.3 for instructions on how immune response values below LLOQ, values above ULOQ and missing values will be handled.

5.5. Safety Analyses

Safety endpoints (secondary endpoints):

- Solicited local (injection site) and systemic adverse events (AEs) for 7 days after vaccination
- Unsolicited AEs for 28 days after vaccination
- Serious adverse events (SAEs) and adverse events of special interest (AESIs) until 6 months after vaccination

Safety analyses will be performed on the FAS. Continuous variables will be summarized using the following statistics, as appropriate: number of observations, median, minimum, and maximum. Frequencies and percentages (one decimal place) will be generated for categorical variables. No formal comparisons between groups will be provided.

Safety data will be analysed and presented by study intervention, and if appropriate, by phase, and also across the entire study period where applicable. For unsolicited AE, the denominator for the percentages is the number of participants in the considered population and phase for a certain regimen (incidence per 100 participants/phase). For solicited AEs, the denominator for the percentages is the number of participants with data assessed by the investigator in the considered population and phase for a certain regimen (incidence per 100 participants/phase).

5.5.1. Adverse Events

5.5.1.1. Definitions

Solicited AEs shown in the tables are extracted from the investigator assessment pages (CE) of the CRF. For unsolicited AEs, only the AEs within the 28-day period following vaccination will be presented in the safety tables except for SAE and potential AESI cases, which will be captured and tabulated in the outputs covering the whole study period. Unsolicited non-serious adverse events collected outside the 28-day period following the vaccination will be presented through listings.

For AESI analyses, the following subcategories are defined:

- Potential AESIs as identified by the investigator
- Potential AESIs selected programmatically

Those will include all reported AEs that are identified by the selection rule:

 SMQ (Standardised MedDRA Queries) = "EMBOLIC AND THROMBOTIC EVENTS (SMQ)"

or

- o (SUB_SMQ1 = "HAEMATOPOIETIC THROMBOCYTOPENIA (SMQ)" and Scope in ("BROAD", "NARROW")) or HLT (higher level term) = "Thrombocytopenias"
- Potential AESIs qualified for assessment

Potential AESIs (programmed/CRF) that have risk levels assessed by one of the following three criteria are considered "qualified for assessment":

- o Brighton Collaboration Level (Level 1-5)
- o CDC Tier (non-tier 1/2, tier 1, tier 2)
- o PRAC criteria (confirmed, possible, probable, unlikely, criteria not met)

Solicited administration site symptoms will be by definition considered as related to the study vaccine.

The severity of the AEs will be classified as grade 1 to 4. Solicited events of grade 0, not reported in the CE domain, will therefore not be reported in the AE analysis.

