AEs and special reporting situations, whether serious or non-serious, that are related to study procedures or that are related to non-investigational sponsor products will be reported from the time a signed and dated informed consent form (ICF) is obtained until the end of the study/early withdrawal. Solicited AEs, collected through a participant diary will be recorded from the time of vaccination until 7 days post-vaccination. All other unsolicited AEs and special reporting situations, whether serious or non-serious, will be reported from the time of vaccination until 28 days post-vaccination. All SAEs, AESIs, and AEs leading to discontinuation from the study (regardless of the causal relationship) are to be reported from the moment of vaccination until completion of the participant's last study-related procedure, which may include contact for safety follow-up. All AEs will be followed until resolution or until clinically stable.

STATISTICAL METHODS

Sample Size Determination

Sample size calculations are performed under the following assumptions:

- a 10% decrease in GMT of the groups with aged lots (Group 2 and Group 3) versus the group with the non-aged lot (Group 1) (ie, assuming a true GMR of Day 15 pre-F ELISA titers equal to 0.9)
- a standard deviation of 1.3 at the log₂ scale for pre-F ELISA on Day 15^a
- a non-inferiority margin of 0.67 (2/3)
- a 2-sided α of 5%
- hierarchical testing (ie, first Group 2 versus Group 1; if non-inferiority is demonstrated, then Group 3 versus Group 1)

A total of 236 evaluable participants per group are needed to have 95% power to demonstrate non-inferiority for each comparison separately. With this sample size, the overall power to demonstrate non-inferiority of Group 3 versus Group 1 as the second comparison in the hierarchy is at least 90%.

To account for exclusions from the Per-protocol Immunogenicity (PPI) Set (see below for the definitions of analysis sets), dropouts, and missing samples, approximately 250 participants per group should be enrolled.

CONFIDENTIAL – FOIA Exemptions Apply in U.S.

^a Based on the standard deviation of pre-F ELISA at 14 days after vaccine administration observed in Group 14 of study VAC18193RSV1004.

Populations for Analysis Sets

The Full Analysis (FA) Set will include all participants who received study vaccine, regardless of the occurrence of protocol deviations. All safety and participant information analyses will be based on the FA Set.

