7. DISCONTINUATION OF STUDY VACCINATION AND PARTICIPANT DISCONTINUATION/WITHDRAWAL

7.1. Discontinuation of Study Vaccination

A participant's study vaccination must be discontinued if:

- The participant withdraws consent to receive study vaccination.
- The investigator believes that for safety reasons or reactogenicity reasons (eg, AE) it is in the best interest of the participant to discontinue study vaccination.

Study vaccine assigned to the participant who discontinued study vaccination may not be assigned to another participant. Discontinuation of study vaccination is only possible between screening and vaccination.

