8.3.1. Time Period and Frequency for Collecting AE, SAE, and AESI Information

All AEs

AEs and special reporting situations, whether serious or non-serious, that are related to study procedures or that are related to non-investigational sponsor products will be reported from the time a signed and dated ICF is obtained until the end of the study/early withdrawal.

Clinically relevant medical events not meeting the above criteria and occurring between signing of ICF and moment of vaccination will be collected on the Medical History eCRF page as pre-existing conditions.

Solicited AEs, collected through a participant diary, will be recorded from the time of vaccination until 7 days post-vaccination.

All other unsolicited AEs and special reporting situations, whether serious or non-serious, will be reported from the time of vaccination until 28 days post-vaccination.

All SAEs and AEs leading to discontinuation from the study (regardless of the causal relationship) are to be reported from the moment of vaccination until completion of the participant's last study-related procedure, which may include contact for safety follow-up. The sponsor will evaluate any safety information that is spontaneously reported by an investigator beyond the time frame specified in the protocol.

See Section 7.2 for procedures associated with withdrawal of consent.

All AEs will be followed until resolution or until clinically stable.

SAEs

All SAEs occurring during the study must be reported to the appropriate sponsor contact person by study-site personnel immediately, but no later than 24 hours of their knowledge of the event.

Information regarding SAEs will be transmitted to the sponsor using the SAE Form and Safety Report Form of the eCRF, which must be completed and reviewed by a physician from the study site, and transmitted to the sponsor immediately but no later than within 24 hours. The initial and follow-up reports of an SAE should be transmitted electronically or by facsimile (fax). Telephone

reporting should be the exception and the reporter should be asked to complete the appropriate form(s) first.

AESIs

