9.4.4. Safety Analyses

No formal statistical testing of safety data is planned. All safety data will be analyzed descriptively by group. All safety analyses will be based on the FA Set.

AEs

The verbatim terms used in the eCRF by investigators to identify AEs will be coded using the Medical Dictionary for Regulatory Activities (MedDRA). All reported AEs with onset during the active phase (ie, AEs occurring from the time of vaccination up to 28 days post-vaccination), and all SAEs and AESIs will be included in the analysis. For each AE, the number and percentage of participants who experience at least 1 occurrence of the given event will be summarized by group.

Summaries, listings, datasets, or participant narratives may be provided, as appropriate, for those participants who die, who discontinue study vaccination due to an AE, or who experience a severe AE, an SAE or an AESI.

Summaries and/or listings may be provided separately for AEs with onset outside the above defined timeframe (ie, beyond 28 days post-vaccination).

Solicited local (injection site) and systemic AEs will be summarized descriptively. The overall frequencies per group as well as frequencies according to severity and duration will be calculated for solicited AEs. In addition, the number and percentages of participants with at least 1 solicited local (injection site) or systemic AE will be presented. Frequencies of unsolicited AEs, separately for all and vaccination-related only, will be presented by System Organ Class and Preferred Term.

Vital Signs

Baseline and emerging vital signs abnormalities will be listed.

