5.5.1.2. Analysis of Adverse Events

Number and percentage of participants with at least one particular AE (unsolicited/solicited) will be tabulated. Unsolicited AEs will be summarized by System Organ Class and Preferred Term. Solicited AEs will be summarized by class (administration site, systemic) and Preferred Term. AESI will be summarized by Interest Category and Preferred Term.

For solicited AEs, the following tables will be provided: summary, by worst severity grade, at least grade 3, related (systemic only), time to onset (in days) and duration (in days). Note: Duration is defined as number of days from the start of the event until resolution of the event. The time to first onset is defined as (date of first onset – reference date + 1). The reference date is the start date of the post-dose period.

A sensitivity analysis for the solicited adverse events will be done. A summary table will be provided by completeness status of e-diary.

A tabulation of the distribution of temperatures per half degree intervals will also be provided.

For unsolicited AEs, the following tables will be provided: summary table (including SAE, fatal outcome, potential AESI and AE leading to study discontinuation), all events, most frequent, at least grade 3, related, AE leading to study discontinuation, SAE, related SAE, potential AESI.

Moreover, table with COVID AEs, potential AESI as identified by the investigator, potential AESIs selected programmatically, and potential AESI qualified for assessment will be created.

Potential AESIs selected programmatically will be tabulated by categories: 'Embolic and thrombotic events (SMQ)' and 'Haematopoietic Thrombocytopenias (SMQ) (broad) or HLT = Thrombocytopenias'. Potential AESI determined programmatically, related to study vaccine (investigator assessment), will be tabulated similarly.

Potential AESIs as identified by the investigator, will be tabulated by categories: 'Embolic and thrombotic events (SMQ)' and 'Haematopoietic Thrombocytopenias (SMQ) (broad) or HLT = Thrombocytopenias', and 'Other'. Potential AESI as identified by the investigator, related to study vaccine (investigator assessment), will be tabulated similarly.

Potential AESIs qualified for assessment will be tabulated by categories: 'Embolic and thrombotic events (SMQ)' and 'Haematopoietic Thrombocytopenia (SMQ) (broad) or HLT=Thrombocytopenias'.

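### AEs leading to study discontinuation are collected to the end of the study, but the SAP tabulates the non-serious, non-AESI ones only within the 28-day period, so that table could be incomplete

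*SAP*

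**What the plan says.** **Collection.** Protocol 8.3.1 states: "All SAEs and AEs leading to discontinuation from the study (regardless of the causal relationship) are to be reported from the moment of vaccination", continuing "until completion of the participant's last study-related procedure, which may include contact for safety follow-up". The synopsis has the same rule: "All SAEs, AESIs, and AEs leading to discontinuation from the study (regardless of the causal relationship) are to be reported". Neither limits the class to serious events. Unsolicited AEs outside these classes stop earlier: "All other unsolicited AEs and special reporting situations, whether serious or non-serious, will be reported from the time of vaccination until 28 days post-vaccination".

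**Tabulation.** SAP 5.5.1.1 says of unsolicited AEs that "only the AEs within the 28-day period following vaccination will be presented in the safety tables except for SAE and potential AESI cases". Non-serious unsolicited AEs collected later go to listings.

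**Planned outputs.** The unsolicited-AE tables in SAP 5.5.1.2 include "at least grade 3, related, AE leading to study discontinuation, SAE, related SAE, potential AESI", and the summary table also has an entry for AEs leading to study discontinuation. No separate time window is given for either.

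**Protocol analysis scope.** Protocol 9.4.4 brings into the analysis AEs with onset up to 28 days post-vaccination, plus all SAEs and AESIs. Summaries or listings of later AEs are optional.

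**The concern.** Three classes of event are followed for the whole study: SAEs, AESIs (including potential AESIs) and AEs leading to study discontinuation. The SAP carries the whole-study window into the tables for the first two and leaves out the third, yet plans a table for it. A programmer applying SAP 5.5.1.1 literally would filter out late non-serious events that caused a withdrawal, although the data are in the database.

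What is at stake is the consistency of a routine tolerability output. Safety and reactogenicity across the three vaccine groups is a secondary objective. SAP 5.2 counts discontinuations and their reasons by group throughout the study. One report could therefore show one number of AE-related withdrawals under disposition and a smaller one in the AE table.

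**Working it through.** The point rests on comparing texts; the plan states no figure for it that could be reproduced.

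**Step 1. Follow each class from collection to table.**

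| Class of unsolicited AE | Collected until (protocol 1.1, 8.3.1) | Tabulated until (SAP 5.5.1.1) |
|---|---|---|
| SAE | last study procedure | whole study |
| AESI, including potential AESI | 6 months (8.3.1); last study procedure for AESIs (synopsis) | whole study |
| AE leading to study discontinuation, neither serious nor a potential AESI | last study procedure | 28-day period |
| Other unsolicited AE | 28 days | 28-day period |

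Only the third row has a table that stops well before collection does.

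**Step 2. Define the omitted events.** SAP 5.5.1.3 allocates AEs by onset. An AE that starts inside the window and leads to withdrawal later is still counted. The omitted set is therefore AEs that are non-serious, are not potential AESIs, start after the window and lead to withdrawal. Protocol 7.2 lists an AE requiring discontinuation as a withdrawal reason, with no time limit, so the set can be non-empty.

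**Step 3. Share of follow-up time outside the table.** Inputs:

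- End of follow-up: the Day 183 visit is 183 − 1 = 182 days post-vaccination. The ±14-day window gives 168 to 196.
- End of tabulation: 28 days. SAP 5.1.2 ends the post-dose period at the later of 28 days and the scheduled 28-day visit. With that visit's +7-day window, the end is at most 28 + 7 = 35 days.

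Share = (end of follow-up − end of tabulation) / end of follow-up:

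- 28-day limit, nominal end: (182 − 28)/182 = 154/182 = 84.6%
- 35-day limit, nominal end: (182 − 35)/182 = 147/182 = 80.8%
- Lowest: (168 − 35)/168 = 133/168 = 79.2%
- Highest: (196 − 28)/196 = 168/196 = 85.7%

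This is a share of calendar time, not of events.

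**Step 4. Possible number of participants.** The documents give no discontinuation rate. As an assumption only, a late risk of 0.1% to 1% per participant would give 750 × 0.001 = 0.75 to 750 × 0.01 = 7.5 participants missing from the table. One participant is 1/250 = 0.4% of a group.

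**Step 5. Does another provision supply the count?** SAP 5.5 allows presentation across the entire study where applicable, but that is general, and 5.5.1.1 is the specific rule with named exceptions. Protocol 9.4.4 permits summaries of later AEs without requiring them. Protocol 9.5 names SAE data to study end for the final analysis and does not name this class. SAP 5.2 does give withdrawal reasons by group for the whole study, but as disposition, not as AE terms.

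**The case against.** The strongest reply is that the SAP follows the protocol's own analysis rule. Protocol 9.4.4 limits the AE analysis to the 28-day phase plus all SAEs and AESIs, and the secondary safety endpoints are framed the same way. Section 8.3.1 governs what is collected and sets no tabulation rule. This stands: a reader might infer that the SAP breaches the protocol's analysis plan, and the documents do not support that. The mismatch is between the collection rule and the table.

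Second, the information is reported elsewhere: in listings, in narratives as appropriate for participants who leave the study because of an AE (SAP 5.5.1.2), and in disposition by group. This also stands, so it would be wrong to say that events are lost or that no whole-study count of withdrawals by group exists. What is missing is their place in the AE table and summary row.

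Third, table titles and windows sit in a separate data presentation specifications document (SAP 1) that is not available here. One cannot say that the table will be mislabelled, only that the SAP states no window for it.

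A reader might also hold that protocol 9.4.4 cannot help, because one of its triggers is participants "who discontinue study vaccination due to an AE, or who experience a severe AE, an SAE or an AESI", while protocol 7.1 says "Discontinuation of study vaccination is only possible between screening and vaccination". The wording does not fit a single-dose study, but a different sentence of 9.4.4 allows summaries of AEs beyond 28 days. The slip is editorial and does not create the gap.

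**Conclusion.** The point holds as a modest, conditional defect. With SAP 5.5.1.1 followed literally, the table and summary row for AEs leading to study discontinuation leave out late-onset, non-serious, non-AESI events that led to withdrawal. If any occur, the table is incomplete and may not match disposition.

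About 81% to 85% of nominal follow-up time falls outside the table for this class (79% to 86% across the visit windows). That must not be read as an undercount of that size: the number of events is unknown and may be zero. Nor do the documents support saying that the tolerability comparison across the groups would be wrong. It would be incomplete if late events occur, and no formal safety comparison is planned. The primary analysis, alpha and sample size are unaffected.

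The conclusion assumes that the specific rule in SAP 5.5.1.1 prevails over the general wording in SAP 5.5, and that the unseen table specifications do not already override it.

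**What to change.** In SAP 5.5.1.1, extend the exception to cover SAEs, potential AESIs and AEs leading to study discontinuation, all tabulated over the whole study period. Adjust the next sentence, on listings for later non-serious AEs, so that it does not pull the same events back out. The table and summary row in SAP 5.5.1.2 then follow. Protocol 9.4.4 already permits summaries of later AEs, so the SAP change needs no protocol amendment.

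If the sponsor prefers to keep the 28-day window, the minimum is to label the table and summary row as limited to that period and add a whole-study count beside them.

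The cost is one clause and the matching table specification. The data are already collected, and no visit, sample or formal analysis changes.

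Optionally, protocol 9.4.4 could refer to discontinuing the study rather than study vaccination because of an AE, as SAP 5.5.1.2 does. That aligns the wording and is not part of the substantive fix.

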5.5.1.2. Analysis of Adverse Events

Number and percentage of participants with at least one particular AE (unsolicited/solicited) will be tabulated. Unsolicited AEs will be summarized by System Organ Class and Preferred Term. Solicited AEs will be summarized by class (administration site, systemic) and Preferred Term. AESI will be summarized by Interest Category and Preferred Term.

For solicited AEs, the following tables will be provided: summary, by worst severity grade, at least grade 3, related (systemic only), time to onset (in days) and duration (in days). Note: Duration is defined as number of days from the start of the event until resolution of the event. The time to first onset is defined as (date of first onset – reference date + 1). The reference date is the start date of the post-dose period.

A sensitivity analysis for the solicited adverse events will be done. A summary table will be provided by completeness status of e-diary.

A tabulation of the distribution of temperatures per half degree intervals will also be provided.

For unsolicited AEs, the following tables will be provided: summary table (including SAE, fatal outcome, potential AESI and AE leading to study discontinuation), all events, most frequent, at least grade 3, related, AE leading to study discontinuation, SAE, related SAE, potential AESI.

Moreover, table with COVID AEs, potential AESI as identified by the investigator, potential AESIs selected programmatically, and potential AESI qualified for assessment will be created.

Potential AESIs selected programmatically will be tabulated by categories: 'Embolic and thrombotic events (SMQ)' and 'Haematopoietic Thrombocytopenias (SMQ) (broad) or HLT = Thrombocytopenias'. Potential AESI determined programmatically, related to study vaccine (investigator assessment), will be tabulated similarly.

Potential AESIs as identified by the investigator, will be tabulated by categories: 'Embolic and thrombotic events (SMQ)' and 'Haematopoietic Thrombocytopenias (SMQ) (broad) or HLT = Thrombocytopenias', and 'Other'. Potential AESI as identified by the investigator, related to study vaccine (investigator assessment), will be tabulated similarly.

Potential AESIs qualified for assessment will be tabulated by categories: 'Embolic and thrombotic events (SMQ)' and 'Haematopoietic Thrombocytopenia (SMQ) (broad) or HLT=Thrombocytopenias'.

All AESI analyses will be presented by phase as well as by time interval. The definition of the different time intervals can be found in Section 5.1.2.

For AESI analyses, attribution to the intervals will be done similarly to the unsolicited AEs as described in Section 5.5.1.3. For Step 2 of phase allocation of adverse events, the '0 - 28 days post-dose' interval should be treated similar to 'active' periods and the rest as 'non-active' periods.

Listings and/or participant narratives will be provided as appropriate, for those participants who die, discontinue study due to an AE, or experience a severe or serious AE or potential AESI.

